
3.3.2. Secondary Objective (*as needed*)

3.3.3. Other Objectives (*as needed*)

3.4. Statistical Interim Analyses

[To outline interim analyses to be conducted and to detail planned adjustment to significance level due to interim analyses]

3.5. Stopping Guidance

[To outline guidelines for stopping the trial early]

3.6. Timing of Final Analysis

The final analyses will be performed following completion of all data collection and processing of all data.

3.7. Timing of Outcome Assessments

The figure below illustrates the timing of outcome assessments across the course of the study, with shading to differentiate measurements in the baseline (light gray), implementation (medium gray), and sustainment (dark gray) phases. Outcome assessments began in the first month of the baseline phase for all sites and clusters. The assessments began, continued on a quarterly basis, and ended at the same points in study time for all sites and clusters. What differed across clusters was the duration of the baseline and sustainment phases, whereas the implementation phase was fixed at 12 months for all sites. Additionally, for all sites and clusters, the first month of the implementation phase included two measurements of MI competence, though by definition, the timing of this varied by cluster.

STANDARD PATIENT INTERACTION SCHEDULE

MONTH	Sep '17	Oct '17	Nov '17	Dec '17	Jan '18	Feb '18	Mar '18	Apr '18	May '18	Jun '18	Jul '18	Aug '18	Sep '18	Oct '18	Nov '18	Dec '18	Jan '19	Feb '19	Mar '19
	0	1	2	3	4	5	6	7	8	9	10	11	12	13	14	15	16	17	18
Block 1 (TN & PA)	X			X	X=2		X			X		X		X				X	
Block 1 (MI & SU)	X			X		X		X=2		X		X		X		X		X	
Block 3 (2)	X		X		X		X		X		X=2		X		X		X		X
Block 4 (2)	X		X		X		X		X			X		X=2		X		X	
Block 5 (2)	X		X		X		X		X			X		X		X		X=2	X
Block 6 (1)	X		X		X		X		X			X		X		X		X	

[figure not shown]
MONTH	Apr '19	May '19	Jun '19	Jul '19	Aug '19	Sep '19	Oct '19	Nov '19	Dec '19	Jan '20	Feb '20	Mar '20	Apr '20	May '20	Jun '20	Jul '20	Aug '20	Sep '20
	19	20	21	22	23	24	25	26	27	28	29	30	31	32	33	34	35	36
Block 1 (TN & ?)			X		X		X		X		X		X		X		X	
Block 1 (MI & SU)			X		X		X		X		X		X		X		X	
Block 3		X		X		X		X		X		X		X		X		X
Block 4		X		X		X		X		X		X		X		X		X
Block 5		X		X		X		X		X		X		X		X		X
Block 6	X=2		X		X		X		X		X		X		X		X	

Color Key

- Light Grey: Baseline Period until Initial Workshop based on randomization
- Medium Grey: Implementation Period (1 year post-first randomization)

- Dark Grey: Sustainment Period (1 year post-second randomization; except Block 5, which ends at 9 months, and Block 6, which ends at 6 months)

Study Timeline:

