6.0 Procedures Involved*

Participants will be part of a multi-phase motivational interviewing (MI) implementation program through the sites where they are employed. MI training will be conducted at sites as part of ongoing professional development.

Participation in the study includes:

PROTOCOL TITLE: TMI

(1) Fidelity Assessments: Quarterly for three years, participants will complete audio recorded standardized patient interactions (a total of 13) over the phone (approximately 30 minutes each) with a study staff member. The study staff member will role play as a patient with HIV and record the session, which will be rated using the MI Coach Rating Scale. This is being done to conduct assessments of their MI skills.

(2) MI training. An MI training workshop will be conducted as part of professional development at the sites. The timing of the training will depend on randomization (two sites are randomized to receive MI training every three months for up to 15 months). Prior to a participant's site's MI training, they will complete standard patient interactions quarterly. While the total number of interactions does not change, the number of interactions they do prior to training depends on their sites randomization and will vary from 2 to a maximum of 6. In the period following initial training, but before the next fidelity assessment, participants will complete two 1-hour coaching sessions over the phone. Following this period, participants may receive additional coaching quarterly for one year following the fidelity assessments described above.

After one year, sites will be randomized to internal facilitation (a person from each site will be chosen to be an MI supervisor to be available for ongoing fidelity monitoring and coaching) plus CoP (the site will decide how to meet as a group to continue MI practice), or to CoP only.

Implementation Teams (iTeams): There will also be an opportunity for some participants to be part of the iTeam at each site. The iTeam will meet monthly to review study progress and make recommendations for how best to implement and sustain MI at each Tailored Motivational Interviewing (TMI) Implementation Intervention site.

Data is formative, longitudinal, qualitative, and quantitative in nature.

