3.2. Randomization

With the DWLD, the 10 sites, in groups of two, were randomly assigned to one of five clusters. To allow sufficient time for scheduling and planning the initial workshop component, each wave of randomization occurred six months prior to the workshop month, which was three months prior to the first pre-intervention fidelity assessment. At each wave of randomization, two of the remaining (i.e., untrained) sites were randomly selected for the next wave of implementation. The specific randomization method involved several steps, each of which was implemented using SPSS software: (1) The full list of sites was entered, (2) each site had a dichotomous Intervention Status indicator (0 = No, 1 = Yes) to reflect whether it had been randomized to the implementation intervention. There were also fields to record the randomization date and initial workshop date. (3) For each wave of randomization, the data were sorted in ascending order by training status and site name. (4) A new random number variable was created for each wave. The assigned random value was obtained using the SPSS random number generator, set using the Mersenne Twister algorithm with a random starting point, and computed using the random uniform function with minimum and maximum values specified as 100000, 999999. (5) After a new random number was assigned to each site, the data were be resorted in ascending order by intervention status and the random number variable. (6) The first two sites (those with the lowest randomly assigned numbers) were selected for the next wave of training. This process was repeated for each subsequent wave of randomization. Drs. [name] and [name] were responsible for implementing the randomization procedure, and TMI study staff were responsible for communicating the randomization results to sites.

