5.2.3. Covariates

	Variable Name (or Calculation/	Definition	Additional Details

	Transformation Specifications if derived)	[to include timings, specific measurements, units of measurement].	(as needed)
Implementation Phase Indicator	PH_IMP	Dummy-Coded Indicator for Measurements in the Implementation Phase	
Sustainment Phase Indicator	PH_SUS	Dummy-Coded Indicator for Measurements in the Sustainment Phase	
Linear Time	L_MO	Linear number of months from the start of the Baseline Phase	
Linear Time, Implementation	L_MO_IM	Linear number of months from the start of the Implementation Phase	
Linear Time, Sustainment	L_MO_SU	Linear number of months from the start of the Sustainment Phase	
Sustainment Phase Condition	COND_IF	Indicator for sites randomized to the CoP with IF condition in the Sustainment Phase	

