5.4.2. Secondary Objective (*as needed*)

5.4.3. Other Objectives (*as needed*)

5.5. Missing Data Procedures

There are two aspects of missing data procedures. The first relates to missing responses to individual items at a given measurement occasion, and the second relates to measurement occasions that are missed entirely by some participants. For TMI, the former is less of a concern, with low rates of observed missingness that can be remedied by standard scoring procedures (e.g., use of average scores rather than total scores). However, given the real-world implementation focus of TMI, there is substantial missingness of measurement occasions across providers. To address this, key considerations include the reasons for missingness, the amount of missingness, the nature of the missingness mechanism, and the resulting statistical remedies.

The primary outcome of MI competency was based on observer ratings across 12 items, and there were no missing item responses; thus, the primary missing data consideration pertains to missed measurement occasions. Across five blocks and ten sites, there were 189 providers. Of these providers, 99% had at least one MI competency measurement in the baseline phase (i.e., prior to the workshop), 75% had at least one measurement during the implementation phase, and 49% had at least one measurement during the sustainment phase. Given the decrease in completed assessments across the three phases, analyses will be performed to determine whether the likelihood of missingness was associated with baseline MI competency or other provider demographic characteristics. A pattern-mixture approach will also be used to determine whether the amount of change between baseline and implementation differed for providers who were missing sustainment data. Combined, the analyses will identify any potential evidence of a non-random missing data pattern that, if identified, can be controlled in subsequent analyses. Assuming there is no evidence of a non-random missingness mechanism, the analytic strategy will be to rely on maximum likelihood estimation, utilization of all available data, and estimation of individual slopes for each provider.

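### The SAP anchors the start of implementation in three different ways; if one workshop-month score is pre-workshop and is coded as treated, the primary phase effect is attenuated

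*SAP*

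**What the plan says.** The documents locate the baseline/implementation boundary in three ways.

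- **By month.** SAP 3.7 states that, for all sites and clusters, "the first month of the implementation phase included two measurements of MI competence". Read literally, both workshop-month scores are implementation scores.
- **By workshop.** The colour key under the same schedule reads "Light Grey: Baseline Period until Initial Workshop based on randomization". SAP 5.5 agrees when it reports that "99% had at least one MI competency measurement in the baseline phase (i.e., prior to the workshop").
- **By randomization.** The next line of the key reads "Medium Grey: Implementation Period (1 year post-first randomization"). SAP 3.2 puts each wave's randomization six months before its workshop month.

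SAP 5.2.3 defines PH_IMP as a "Dummy-Coded Indicator for Measurements in the Implementation Phase" and L_MO_IM as months from the start of that phase. Neither definition has a cut-off date or a rule for the workshop month. SAP 5.1.5 analyses each score in the phase of its measurement occasion, so the phase label is the exposure. SAP 5.4.1 makes the phase indicators and time polynomials the primary parameters.

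On the order of events, Protocol 6.0 has quarterly interactions, workshops every three months for up to 15 months, and a number of pre-training interactions that "will vary from 2 to a maximum of 6". SAP 3.2 says of the randomization date: "which was three months prior to the first pre-intervention fidelity assessment".

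**The concern.** The three anchors give the same coding only in special cases. If one of the two workshop-month interactions was held before training, the 3.7 sentence makes it an implementation score (PH_IMP = 1, L_MO_IM = 0), while the key's first line and 5.5 make it a baseline score. Nothing says which rule prevails.

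The first primary hypothesis is the rise in competency from baseline to implementation. An untreated score coded as treated pulls that contrast towards zero if the true effect is a positive step. It can also make an immediate jump look like growth within the phase, which is what the second stage of 5.4.1 tests.

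There is a side effect on who contributes. Protocol 5.0 lets providers continue beyond baseline only if they attended at least half of the workshop. Under month-based coding, a provider who failed that rule could enter the implementation phase with a single score, taken before any training.

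**Working it through.** **1. The plan's own figures.** The documents give no figure for misclassification. The nearest are the power figures in SAP 3.3.1, with n_eff = n / [1 + (m − 1)ρ]:
- Measurements within providers: 1237 / [1 + (6.545 − 1) × 0.35] = 420.6, which matches 420 (m = 1237/189).
- Providers within sites: 420 / [1 + (42 − 1) × 0.09] = 89.6, which matches 90 (42 = 420/10 sites).
- Power at R² = .09, N = 90, one predictor, two-sided α = .05 (sidedness assumed): 0.84.

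**2. Is one workshop-month score pre-workshop?** Take quarterly visits from month 0 and workshops at months 3, 6, 9, 12 and 15.
- Visits in months before the workshop month: 1, 2, 3, 4, 5.
- Adding one pre-training visit in the workshop month: 2, 3, 4, 5, 6, which is Protocol 6.0's range.
- SAP 3.2 puts the first pre-intervention assessment three months before the workshop month (6 − 3 = 3). For the first wave, the next quarterly visit then falls in the workshop month.
- The protocol total of 13 does not discriminate. Visits at months 0 to 33 plus one extra give 12 + 1 = 13; visits at months 0 to 36 without an extra also give 13.
- The printed schedule does not settle it. Its first two rows show 2 and 3 marks before the double entry, which also fits both scores being post-workshop. Its columns are garbled and the marks are not quarterly.

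**3. Effect of coding that score PH_IMP = 1.** Assume a true step of 1.0 at the workshop, sustained, with no secular trend. Quarterly visits over a 12-month implementation phase give five coded scores at months 0, 0, 3, 6 and 9, the first untreated.
- Phase mean: 4/5 = 0.80. If month 12 also counts, 5/6 = 0.83.
- Straight line through (0, 1, 1, 1, 1) at those months: intercept 0.588, slope 0.0588 per month, or 0.0588 × 12 = 0.71 per year. The true values are 1.0 and 0.

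Generalized least squares with a provider intercept (ICC .35, from 3.3.1) and cluster indicators gives this recovered fraction of the true implementation step:

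| Model | Complete data | Attrition tuned to 3.3.1 and 5.5 | Dropout spread evenly |
|---|---|---|---|
| Phase indicators only | 0.80 | 0.70–0.72 | 0.75–0.78 |
| Plus common linear time | 0.58–0.68 (last visit month 30–36) | 0.50–0.51 | 0.54–0.58 |
| Plus phase-specific slopes | 0.59 | 0.51 | 0.55–0.59 |

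Coding the score as baseline returns 1.00 in every complete-data model, and 0.97 to 1.03 in the attrition simulations behind the table, which is simulation error.

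The attrition columns are simulations and their dropout patterns are assumptions. The tuned one has 70% of visits completed, 22% leaving at the workshop and an 8% quarterly hazard afterwards. It gives about 6.7 measurements per provider, with 75% having implementation data and 54% sustainment data (5.5 reports 75% and 49%). About 27% of implementation-coded scores are then untreated. The even-dropout patterns leave 89–92% with implementation data, so they match 5.5 less well.

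**4. If the gain is gradual.** Let it start at zero at the workshop and rise linearly. The untreated score then lies on the fitted line at L_MO_IM = 0, and the piecewise model has no bias. The phase-mean contrast still shrinks: mean months since workshop are 18/5 = 3.6 with the extra score and 18/4 = 4.5 without it, a ratio of 0.80.

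**5. Power on the SAP's basis.** Scaling the effect by d gives R² = 0.09d² / (0.91 + 0.09d²). Power is 0.66 at d = 0.80, 0.41 at 0.59 and 0.31 at 0.50. This is illustrative, because 3.3.1 itself notes that its method ignores the number of parameters.

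**The case against.** The premise is never stated. No sentence in either document says that a workshop-month score precedes the workshop. If both follow it, 3.7, the first line of the key and 5.5 agree. This stands, and it makes the miscoding conditional.

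A workshop-based definition already exists in 5.5, next to phase counts that were apparently made with it, and the 3.7 sentence may be describing the schedule rather than setting a coding rule. The randomization line of the key may likewise be loose labelling. This also stands as far as it goes, but no text gives 5.5 precedence. SAP 5.3 leaves phase configuration to preliminary analyses. Which side of training a score falls on is a matter of dates and should not be chosen from outcome data.

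Two stronger readings are tempting. A reader might infer that the last untreated score of every provider will be coded as treated. The documents do not support this: it needs 3.7 to override 5.5, and occasions were often missed. A reader might also infer that the primary effect is roughly halved. That is the upper end only. It needs time terms plus an assumed attrition pattern, and 5.4.1 tests the level shift before the rate of change while 5.3 leaves the form of time open.

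The step effect is itself an assumption. Training is followed by two coaching sessions and further quarterly coaching, so a gradual gain is plausible, and step 4 shows that the piecewise model then has no bias. Finally, for a positive step the bias on the level shift is conservative. The spurious within-phase slope is not.

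**Conclusion.** The definition of the phase boundary is inconsistent and needs correction. That one workshop-month score is pre-workshop is a sound inference from Protocol 6.0 and SAP 3.2, but it remains an inference. If it is right and 3.7 governs the coding, an immediate, sustained step is underestimated by about 20% (phase indicators only, complete data) to 30% (assumed attrition). With time terms in the model the loss is 32–42% with complete data and reaches about 50% only under the tuned attrition pattern. These sizes assume workshops at months 3 to 15, exactly quarterly visits and no secular trend. Under a gradual gain the piecewise model is essentially unbiased. The documents do not show that scores have been or will be miscoded.

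**What to change.** 1. In SAP 5.2.3, define PH_IMP = 1 only for interactions held after the provider's site workshop, and set the zero of L_MO_IM at that site's actual workshop date. Any interaction held before the workshop, including one in the workshop month, is baseline (PH_IMP = 0, L_MO_IM = 0).
2. In SAP 3.7, state the order of the two workshop-month measurements relative to the workshop and the phase of each.
3. Reconcile the colour key so that implementation is dated from the workshop rather than from first randomization, and use the same definition in 5.5.
4. If both measurements are post-workshop, state that; no result changes.

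The cost is a few sentences in the SAP and, at most, a recode from the assessment dates and the workshop dates that SAP 3.2 says are recorded. No new data are needed, and the rule is harmless whichever order proves true.

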4. STUDY POPULATION

4.1. Study Population Characteristics

[Organized by objective (if different by objective)]

[To briefly outline study population characteristics; to include but not to be limited to:

- *Demographic characteristics*
- *Medical history*
- *Other background characteristics]*

4.1.1. Primary Objective

4.1.2. Secondary Objective (as needed)

4.1.3. Other Objectives (as needed)

4.2. Screening Data

NA

4.3. Eligibility Criteria

Inclusion Criteria:

All youth HIV providers (prevention and care) at our target sites that meet a minimum of four hours per week of patient contact are eligible to participate.

Exclusion Criteria:

Clinic personnel that have limited to no patient contact are excluded.

4.4. Recruitment

[To describe information to be included in the CONSORT flow diagram]

TMI study staff will work with the SC at each site to introduce the project and recruit participants by scheduling and conducting introductory meetings (via phone) with the SC and site PI and clinic staff. After the introductory meetings, the SC or PI from each site will send contact information (email, phone number) to the TMI study staff. The TMI study staff will contact participants via email and/or phone call to provide the information sheet and schedule of assessments. TMI study staff will also work with the SC and site PI to schedule the MI training session(s).

4.5. Withdrawal and Lost to Follow-Up

[To outline withdrawal/lost to follow-up details including but not limited to:

- *How withdrawal/lost to follow-up will be defined*
- *Level of withdrawal (e.g. from intervention and/or follow-up)*
- *Timing of withdrawal/lost to follow-up data*
- *Reasons and details of how withdrawal/lost to follow-up data will be presented]*¹

4.5.1. Withdrawal

4.5.2. Lost to Follow-up

TMI Study staff who no longer wish to participate in follow-ups are lost to follow-up.

5. STATISTICAL ANALYSIS

5.1. Statistical Principles

5.1.1. Confidence Intervals and P-values

The test statistical for estimated effects will be the Wald statistic (i.e., β / SE), evaluated relative to a threshold of $p < .05$. To reflect the magnitude and precision of the unstandardized effect, 95% confidence intervals will be computed and reported for all estimated effects. To address multiple testing, planned contrasts will be specified to obtain all comparisons of interest from a single model for each outcome.

5.1.2. Descriptive Statistics

Standard descriptive statistics will be computed in preparation for final data analyses, and of these, the most relevant descriptive statistics will be included in the main outcome manuscript. Continuous variables will be described based on the mean, median, standard deviation,

minimum, and maximum; and categorical variables will be described based on observed frequencies across the range of possible categories.

5.1.3. Adherence to Intervention

[To specify details related to adherence to intervention including but not limited to:

- *Definition of adherence to the intervention and how this will be assessed including extent of exposure*
- *Duration of intervention exposure*
- *Description of how adherence to the intervention will be presented]*²

5.1.4. Protocol Deviation

[To specify details related to protocol deviation including but not limited to:

- *Definition of protocol deviations*
- *Description of which deviations will be summarized]*²

5.1.5. Analysis Population

Intention-to-treat analyses will be performed, with each provider retained in the original site, cluster, and intervention phase corresponding to the measurement occasion.

5.2. Specification of Key Variables

5.2.1. Outcomes

	Outcome Type [e.g. primary, secondary, etc.]	Variable Name [To include Calculation/Transformation Specifications, if derived]	Definition [to include reference to definition or name of author/coauthor that provided definition. To specify timings, specific measurements, units of measurement.]	Primary/Key Secondary Endpoints [if applicable; listed in order of importance]	Algorithm for Value Calculation in Case of Partially Complete Data
MI Competency, Raw Average Score	Primary	MICRS_AV	MI Competency, Raw Average Score on the 12-Item MI Coach Rating Scale		Mean(MIRating1 to MIRating 12)

			(MI-CRS), Ranging from 1-4		
MI Competency, Criterion Score	Primary	MICRS_CR	MI Competency Level, Criterion Score (Beginner, Novice, Intermediate, Advanced), Ordered Categorical Criterion Score Based on Defined Thresholds for Competency Raw Scores		
HIV Care Cascade Related Outcomes, ***	Secondary	Viral Load			
...					

5.2.2. Exposures

	Exposure Type [e.g. primary, secondary, etc.]	Variable Name [to include calculation/ transformation specifications, if derived]	Definition [to include timings, specific measurements, units of measurement]	Additional Details (as needed)
[Exposure A]				
[Exposure B (as needed)]				
[Exposure C (as needed)]				
...				

